6.1.4 Treatment duration

After inclusion in the study, each patient will be dosed b.i.d. with study drug for 3 days (at the following time points: 0, 8, 24, 36, 48 and 60 hours) under hospital supervision.

Patients may be discontinued from treatment at the discretion of the investigator or of the parents/legal guardian or due to:

- Disease progression (see [Section 6.2.3](#))
- Use of prohibited treatment (see [Table 6-2](#))

- Any situation in which study participation might result in a safety risk to the patient and/or any adverse events that in the judgement of the investigator, taking into account the patient's overall status, prevent the patient from continuing participation in the study
- Deviation from the planned dose regimen for the study drug, for instance, if the patient vomits a dose within 1 hour of intake, as well as its replacement dose within 1 hour of intake.

6.2 Other treatment(s)

6.2.1 Concomitant therapy

Concomitant medication is defined as any medication, other than the study drug, which is given at least once between the day of first dose of study medication and the last visit of core follow-up period (including those which were started pre-baseline and continued into the treatment period), including prescription and over-the-counter medicines, and any traditional or herbal remedies.

The investigator should instruct the patient's legal guardian to notify the study site about any new medications the patient takes after the start of the study drug. All medications and significant non-drug therapies (including physical therapy and blood transfusions) administered after the patient starts treatment with study drug must be recorded on the appropriate CRF.

Similarly, all medications and significant non-drug therapies administered during the core follow-up period to a mother breastfeeding a patient after the patient starts treatment with study drug must be listed on the appropriate CRF.

Each concomitant drug must be individually assessed against all exclusion criteria/prohibited medication. If in doubt, the investigator should contact the Novartis medical monitor before entering a subject in the study or allowing a new medication to be started during the study. If the subject is already recruited, the investigator should also contact Novartis to determine if the subject should continue participation in the study.

6.2.1.1 Permitted concomitant therapy requiring caution and/or action

The following should be used with caution, i.e. with staggered dosing (unless already listed in [Section 6.2.2](#)) during the core follow-up period (6 weeks)

- **CYP3A4 inhibitors:** The concurrent oral administration of ketoconazole with artemether-lumefantrine 20 mg:120 mg led to a modest increase (≤ 2 -fold) in artemether, DHA, and lumefantrine exposure in healthy adult subjects. This was not associated with increased side effects. However, there is a potential for increased concentrations of lumefantrine which could lead to QT prolongation,
- **Weak to moderate inducers of CYP3A4:** When artemether:lumefantrine 20 mg:120 mg is co-administered with weak to moderate inducers of CYP3A4, it may result in decreased concentrations of artemether and/or lumefantrine and lower the antimalarial efficacy. Patients can experience this interaction even while they or the mother/breastfeeding person stops treatment around 2 weeks before the patient starts taking artemether-lumefantrine.

These restrictions result from potential interactions with study drug.

6.2.2 Prohibited medication

For the period(s) specified, use of the treatments displayed in [Table 6-2](#) is not allowed in:

- patients
- the person providing breastmilk to the patients (as the prohibited drug is known to be secreted significantly in breastmilk), except for antimalarials or antimicrobials with antimalarial activity.

These restrictions result from potential confounding of efficacy or from drug interaction.

Table 6-2 Prohibited medication

| Medication* | Prohibition period** | Action taken*** |
|--|---|--|
| Drugs that are known to prolong the QTc interval such as: 
• antiarrhythmics of classes IA and III• neuroleptics, antidepressant agents• certain antibiotics including some agents of the following classes: macrolides, fluoroquinolones, imidazole, and triazole antifungal agents• certain non-sedating antihistaminics (terfenadine, astemizole)• cisapride | At least 5 times their half-life before study entry and at least for 28 days after last AL dose | Discontinue prohibited medication, monitor patient closely for any cardiac event, discontinue the study treatment in case of cardiac event |
| Drugs which are metabolized by the cytochrome enzyme CYP2D6 especially those with a narrow therapeutic index e.g. flecainide, metoprolol, imipramine, amitriptyline, clomipramine | At least for 28 days after last AL dose | Discontinue prohibited medication, monitor for potential effects of overexposure of impacted drug. However patients taking one of these drugs should stay in the study and follow-up visits for efficacy should be performed according to the visit schedule, i.e. remaining visits for the entire core study period (until Day 43), and the follow-up visit at 12 months of age |

| Medication* | Prohibition period** | Action taken*** |
|---|--|--|
| inducers of CYP3A4 Strong inducers of CYP3A4 like rifampicin and St. John's wort can reduce the exposure of artemether and lumefantrine to a clinically significant level | At least 5 times their half-life plus two weeks before study entry and during entire core study period (until Day 43) | Discontinue prohibited medication. However patients taking one of these drugs should stay in the study and follow-up visits for efficacy should be performed according to the visit schedule, i.e. remaining visits for the entire core study period (until Day 43), and the follow-up visit at 12 months of age |
| Herbal medication | Entire core study period (until Day 43) except as rescue medication | Discontinue study treatment. However, patients taking one of these drugs should stay in the study and follow-up visits for efficacy should be performed according to the visit schedule, i.e. remaining visits for the entire core study period (until Day 43), and the follow-up visit at 12 months of age |
| Antimalarials other than the study drug | At least 5 times their half-life before study entry and during entire core study period (until Day 43) except as rescue medication | Discontinue study treatment. However, patients taking one of these drugs should stay in the study and follow-up visits for efficacy should be performed according to the visit schedule, i.e. remaining visits for the entire core study period (until Day 43), and the follow-up visit at 12 months of age |
| other ACTs: e.g. artesunate-amodiaquine (ASAQ), artesunate-pyronaridine, DHA-piperaquine chloroquine, amodiaquine quinine, quinidine mefloquine, halofantrine, lumefantrine as monotherapy artemisinin and its derivatives used as monotherapy: artemether, arteether, artesunate, dihydroartemisinin proguanil, chlorproguanil, pyrimethamine sulfadoxine, sulfalene, sulfamethoxazole, dapsone primaquine atovaquone | | |

| Medication* | Prohibition period** | Action taken*** |
|--|---|--|
| Other antimicrobials with antimalarial activity antibiotics: tetracycline****, doxycycline, erythromycin, azythromycin, clindamycin, rifampicin, trimethoprim pentamidine | entire core study period (until Day 43) except as rescue medication | Discontinue study treatment. However patients taking one of these drugs should stay in the study and follow-up visits for efficacy should be performed according to the visit schedule, i.e. remaining visits for the entire core study period (until Day 43), and the follow-up visit at 12 months of age |

* applicable to the patient AND the person breastfeeding the patient

** based on the patient's time point of inclusion in the study

*** applicable to the patient (except for prohibited drug discontinuation)

****Topical tetracycline can be used.

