9.1 Discontinuation

9.1.1 Discontinuation of study treatment

Discontinuation of study treatment for a subject occurs when study treatment is stopped earlier than the protocol planned duration and can be initiated by either the subject's parent/legal guardian or the investigator.

The investigator must discontinue study treatment for a given subject if they believe that continuation would negatively impact the subject's well-being.

Study treatment must be discontinued under the following circumstances:

- Subject's parent/legal guardian decision
- Use of prohibited treatment as per recommendations in the prohibited treatment section
- Any situation in which study participation might result in a safety risk to the subject
- Adverse events, abnormal laboratory values, or abnormal test result that indicate a safety risk to the subject (see [Section 16.1-Appendix 1](#)). For liver, see [Section 16.2-Appendix 2](#).
- Unsatisfactory therapeutic effect
- Any laboratory abnormalities that in the judgment of the investigator, taking into consideration the subject's overall status, prevents the subject from continuing participation in the study

Subjects who discontinue study treatment or whose parent/legal guardian decide they do not wish their child to participate in the study further should NOT be considered withdrawn from the study UNLESS they withdraw their consent (see 'Withdrawal of Informed Consent' section).

Where possible, they should return for the assessments indicated in the Assessment Schedule. If they fail to return for these assessments for unknown reasons, every effort (e.g., home visit) should be made to contact the subject's pre-designated contact as specified in the lost to follow-up section. This contact should preferably be done according to the study visit schedule.

If the parent/legal guardian cannot or is unwilling to have the subject attend any visit(s), the site staff should maintain regular contact with them, or with a person pre-designated by them. This contact should preferably be done according to the study visit schedule.

The investigator must also contact the IRT to register the subject's discontinuation from study treatment.

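### The Table 6-2 footnote contradicts the Section 6.2.2 exemption for the breastmilk provider's antimalarials and, read literally, would stop the infant's treatment for a permitted maternal drug

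*Protocol*

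**What the plan says.** Section 6.2.2 of the protocol forbids the drugs in Table 6-2 to patients and to the person providing breastmilk. For the provider it makes one exception: "except for antimalarials or antimicrobials with antimalarial activity".

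The table's own footnotes read differently. The single-asterisk footnote, on the medication column, is "applicable to the patient AND the person breastfeeding the patient" and has no exception. The triple-asterisk footnote, on the action column, is "applicable to the patient (except for prohibited drug discontinuation". So the consequence falls on the infant, and only the stopping of the prohibited drug can fall on someone else.

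The exempted drugs fill two rows: antimalarials other than the study drug, and other antimicrobials with antimalarial activity. The action in the first is "Discontinue study treatment. However, patients taking one of these drugs should stay in the study", and the second says the same apart from a comma.

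Two other sections lead to this material:
- Section 6.1.4 lists use of prohibited treatment among the reasons for which a patient may be discontinued, and cites Table 6-2 by number.
- Section 9.1.1 makes discontinuation mandatory for "Use of prohibited treatment as per recommendations in the prohibited treatment section".

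Rifampicin is named twice in the table. One row begins "Strong inducers of CYP3A4 like rifampicin", and the antimicrobial row lists it again.

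**The concern.** Table 6-2 is an operative stopping rule, and Section 6.2.1 has sites assess every concomitant drug against the prohibited list. It also has them record what a breastfeeding mother takes, so the table will be consulted for her drugs as well as the infant's. A reader who works from the table and its footnotes would conclude that her antimalarial stops the infant's course. A reader of the paragraph above the table would conclude that it does not.

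At stake is an infant under 5 kg with *P. falciparum* malaria losing part of a six-dose course for no reason that the protocol intends. Cohort 2 admits congenital malaria, so treatment of the mother is foreseeable. That is an inference, because the documents give no frequency. Any effect on the analysis is secondary to this.

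**Working it through.** **1. One case under both readings.** Suppose (my assumption, for illustration) that a breastfeeding mother takes an antimalarial 30 h into the infant's course.

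| Text followed | Is her drug prohibited? | Consequence for the infant |
|---|---|---|
| Section 6.2.2, body | No, exempt | None; doses at 36, 48 and 60 h are given |
| Table 6-2 with its footnotes | Yes, the row covers her | Study treatment stopped after the doses at 0, 8 and 24 h, i.e. 3/6 = 50% |

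The two texts cannot both be followed. The footnote goes beyond leaving the exemption out: it states a scope that the exemption denies.

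**2. When a stop can act.** Doses are given at 0, 8, 24, 36, 48 and 60 h (Section 6.1.4), so after the 60 h dose there is nothing left to stop. Artemether Cmax is the higher of the 1 h and 2 h concentrations after the first dose, so a later stop does not touch it.

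**3. Tablets and the per-protocol set.** SAP Section 2.4.1 gives 12 planned tablets at dose level 2, which is 2 per dose. SAP Section 2.2 requires at least 80% of study medication.
- Stop before the 48 h dose: at most 4 doses, 8/12 = 66.7%, below the threshold.
- Stop between the 48 h and 60 h doses: 5 doses, 10/12 = 83.3%, above it.

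The tablet count is not the only route out. SAP Section 5.8 also excludes patients for the prohibited-medication deviations PROH01A and PROH02, whatever the number of doses taken. The SAP does not say whether a provider's drug would be recorded as one of these.

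**4. Size of one loss.** If all n patients respond, the Clopper-Pearson lower 95% limit is 0.025^(1/n).
- n = 22: 0.025^(1/22) = 0.8456
- n = 21: 0.025^(1/21) = 0.8389

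The difference is 0.67 percentage points.

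**5. Day 8 lumefantrine.** The PK set has no dose-count criterion. An infant stopped early could therefore remain in the key secondary analysis with a concentration from a shortened course, unless it is judged not evaluable. The SAP does not define evaluable here, so this effect cannot be sized.

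**6. Infants still exposed to the rule.** Amendment 1 reports 3 patients in Cohort 2.1 and 2 in Cohort 2.2 as of 29-Jun-2023. Against about 22 planned, 22 − 3 − 2 = 17 remained, if no dose is re-run and enrollment does not stop early.

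**7. Rifampicin, row against row.**

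| Row | Period | Action |
|---|---|---|
| CYP3A4 inducers | 5 half-lives plus two weeks before entry, then to Day 43 | Stop the prohibited drug; patient stays in the study |
| Antimicrobials | Core period to Day 43, except as rescue | Stop study treatment; patient stays in the study |

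For an infant, both rows can be carried out together. For the provider they diverge. Rifampicin is listed as an antimicrobial with antimalarial activity, so Section 6.2.2 exempts it. It is also listed as a strong inducer, and that row covers the provider.

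**The case against.** The strongest reply is that the exemption already stands where it governs. Table 6-2 sits inside Section 6.2.2, under the sentence that carries the exemption, and a general footnote would normally be read subject to a specific exception. The mandatory rule in Section 9.1.1 points to the section as a whole, exemption included. Section 6.1.4 does cite the table by number, but it is permissive. The action cells speak of patients who take the drug. Section 6.2.1 also provides for doubtful cases: "If the subject is already recruited, the investigator should also contact Novartis to determine if the subject should continue participation in the study".

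All of this stands, and it makes an actual wrongful stop unlikely. It does not reconcile the two texts. The sponsor contact is triggered by doubt, and a site that reads an unqualified footnote may have none.

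A reader might infer that the two rifampicin rows give opposite orders, one to continue study treatment and one to stop it. The documents do not support that. The inducer row says nothing about continuing study treatment. Its wording about staying in the study also appears in the row that stops treatment, so it refers to follow-up. The periods are cumulative as well, since both rows run to Day 43 and one adds a pre-entry washout. What remains open is the provider's rifampicin. Nor can one simply say that it stays prohibited, because Section 6.2.2 read with the antimicrobial row literally exempts it.

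**Conclusion.** The contradiction is real, and the table is wrong as written. The body text is the evident intent, and the practical risk is small. A wrongful stop needs a site to follow the footnote over the paragraph above it and not to call the sponsor, within the dosing window of at most 60 h in hospital. The primary endpoint, the sample size and the planned methods are unaffected. One lost per-protocol patient moves a confidence limit by 0.67 points (assuming 22 patients, all responding), which is negligible. The reason to act is the infant's treatment.

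A reader might infer from the 80% threshold that per-protocol loss occurs only if the stop comes before the 48 h dose. That does not follow, because the deviation criteria in SAP Section 5.8 can exclude a patient at any dose count. The number of infants who might be affected cannot be computed, because the documents do not say how often providers take these drugs.

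The rifampicin overlap is a lesser matter that needs clarification.

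**What to change.** At the next protocol amendment:

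1. Extend the single-asterisk footnote of Table 6-2 so that it reads: "applicable to the patient AND the person breastfeeding the patient", except the rows for antimalarials other than the study drug and for other antimicrobials with antimalarial activity, which apply to the patient only. This restores the sponsor's own exemption.
2. Add a line saying whether the provider's rifampicin is exempt under Section 6.2.2 or barred as a strong CYP3A4 inducer. The footnote edit does not settle this, because it exempts rows while the body text exempts drugs. The choice is the sponsor's.
3. Add that where a drug falls in several rows, the strictest period and action apply. This also covers erythromycin, which is in the antimicrobial row and belongs to the macrolides mentioned in the QTc row.

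The cost is one footnote edit and two lines. Section 14.1 requires a written amendment with IRB/IEC approval, and health authority approval where required. Section 5 gives about 10 sites in 8 countries, so this belongs in the next amendment and does not justify one of its own. Design, sample size and analysis stay as they are.

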6.2.3 Rescue medication

The following circumstances warrant discontinuation of study treatment (during the treatment period) and the implementation of rescue medication by the investigator (Commencement of rescue medication may occur after the start of study drug and up to Day 43):

Early Treatment Failure (ETF)

- Development of danger signs or severe malaria on Day 2, Day 3, Day 4 in the presence of parasitemia.
- Parasitemia on Day 3 higher than Day 1 count irrespective of axillary temperature.
- Parasitemia on Day 4 with axillary temperature $\geq 37.5^\circ$.
- Parasitemia on Day 4 equals to or more than 25% of count on Day 1.

Late Clinical Failure (LCF)

- Development of danger signs or severe malaria on any day from Day 5 to Day 43 in the presence of parasitemia without previously meeting any of the criteria of Early Treatment Failure.
- Presence of parasitemia and axillary temperature $\geq 37.5^\circ$ on any day from Day 5 to Day 43 without previously meeting any of the criteria of Early Treatment Failure.

Late Parasitological Failure (LPF)

- Presence of parasitemia on any day from Day 8 to Day 43 and axillary temperature $< 37.5^\circ$ without previously meeting any of the criteria of Early Treatment Failure or Late Clinical Failure.

Rescue treatment involves therapy with an effective antimalarial available locally as per local medical practice or National Treatment Guidelines. Administration may be oral or parenteral depending on the subject's clinical condition. Rescue treatment will not be considered study medication. The exact rescue regimen and route of administration must be recorded on the appropriate CRF.

Patients will be monitored, either in clinic, or via home visits for the duration of treatment to ensure adherence to the rescue medication therapy. These patients will not discontinue the study (i.e., all the examinations as per the assessment schedule and all CRF for this patient will need to be completed), and they will not be replaced (unless the PK data cannot be properly analyzed due to treatment schedule discontinuation).

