12.5.1 Efficacy and/or Pharmacodynamic endpoint(s)

Secondary Efficacy variables are:

- PCR-corrected ACPR at Day 15, Day 29 and Day 43.
- Uncorrected ACPR at Day 8, Day 15, Day 29, and Day 43.
- Incidence rate of recrudescence and new infections at Days 15, 29 and 43
- Parasite and Fever clearance Times (PCT and FCT)

At each visit, the ACPR rate with 95% confidence intervals will be provided using the Pearson-Clopper method for each treatment group by cohort using PPS for PCR-corrected ACPR and FAS for uncorrected ACPR. Data will be handled as follows:

- Treatment failures after 7 days (i.e., Study Day 8) due to new infections based on PCR genotyping are not considered as failure for PCR-corrected analyses.

- For uncorrected ACPR, patients will be treated as failure on and after the visit when a reinfection with *P. falciparum* or other species is detected (which might be either recrudescence or a new infection).
- Patients who received rescue medication for the treatment of *P. falciparum* malaria (except for the treatment of a new infection) will be considered treatment failures. Patients who received other concomitant medication having an effect on malaria for reasons other than rescue therapy e.g., for the treatment of *P. vivax* (e.g., primaquine, certain antibiotics (sulfonamides, tetracycline, etc.) will be considered in the analysis as if they had not taken the drug.
- Patients will be counted as failure at a visit (e.g. Study Day 15, etc.) if (a) they did not have a parasite count, i.e., missing parasite count at that visit unless these patients could be classified as cured based on absence of parasitemia (parasite count = 0) at a later time (e.g., Study Day 29), or (b) they did not have valid PCR evaluations at baseline and the visit if parasitaemia was present at that time (e.g., Study Day 15).
- For intermediate missing data, (a) once a patient experienced a treatment failure at a timepoint (eg. Day 15), the patient is considered as treatment failure at all later timepoints (eg. Day 29), (b) if a patient is considered as cured at a timepoint (eg. Day 29), the patient is considered as cured at earlier timepoints (eg. Day 15).

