2.7.2.1 PCR-corrected ACPR and uncorrected ACPR

At each visit, the ACPR rate with 95% 2-sided confidence intervals will be provided using the Clopper-Pearson method for each treatment group by cohort using PPS for PCR-corrected ACPR and FAS for uncorrected ACPR.

Data will be handled as follows:

- Treatment failures after 7 days (i.e., Study Day 8) due to new infections based on PCR genotyping are not considered as failure for PCR-corrected analyses.

- For uncorrected ACPR, patients will be treated as failure on and after the visit when a reinfection with *P. falciparum* or other species is detected (which might be either recrudescence or a new infection).
- Patients who received rescue medication for the treatment of *P. falciparum* malaria (except for the treatment of a new infection) will be considered treatment failures. Patients who received other concomitant medication having an effect on malaria for reasons other than rescue therapy e.g., for the treatment of *P. vivax* (e.g., primaquine, certain antibiotics (sulfonamides, tetracycline, etc.) will be considered in the analysis as if they had not taken the drug.
- Patients will be counted as failure at a visit (e.g. Study Day 15, etc.) if (a) they did not have a parasite count, i.e., missing parasite count at that visit unless these patients could be classified as cured based on absence of parasitaemia (parasite count = 0) at a later time (e.g., Study Day 29), or (b) they did not have valid PCR evaluations at baseline and the visit if parasitaemia was present at that time (e.g., Study Day 15).
- For intermediate missing data, (a) once a patient experienced a treatment failure at a timepoint (eg. Day 15), the patient is considered as treatment failure at all later timepoints (eg. Day 29), (b) if a patient is considered as cured at a timepoint (eg. Day 29), the patient is considered as cured at earlier timepoints (eg. Day 15).

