2.7.2.1.1 Analysis of PCR-corrected ACPR using Kaplan-Meier method

In addition, PCR-corrected ACPR rate will be calculated and plotted using the Kaplan-Meier method ([Stepniewska and White 2006](#); [WHO 2015](#)) for each treatment group by cohort in the FAS for Study Day 29 and 43. The PCR-corrected ACPR rate at Study Day 29 (43) is estimated by the survival function at Study Day 29 (43).

Event is defined as treatment failure. The censoring rules are as follows:

- For patients who do not experience treatment failure and do not have Study Day 43 data, time to treatment failure is considered as censored at the time of last parasitaemia assessment.
- Patients who had a new infection with *P. falciparum* or other species without *P. falciparum* recrudescence on or after Study Day 8 will be censored at the time of the first PCR that indicate the infection.
- Patients who took antimalarial medications for reinfection or reasons other than rescue medication given for *P. falciparum* related treatment failure will be censored at the first time of such antimalarial medications.
- Time to treatment failure (event or censored) will be truncated at Day 43 to avoid sudden drop in number of patients at risk after Day 43.

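### Uncorrected ACPR ignores a non-rescue drug with antimalarial effect even when that drug ended the study course, while other analyses in the SAP censor or exclude the same infant; a sensitivity analysis is needed

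*Protocol*

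**What the plan says.** **Stopping rule.** In protocol Table 6-2, the rows for herbal medication and for other antimalarials carry the action "Discontinue study treatment. However, patients taking one of these drugs should stay in the study and follow-up visits for efficacy should be performed". The row for antimicrobials with antimalarial activity has the same action. All three exempt rescue use; the herbal row's period reads "Entire core study period (until Day 43) except as rescue medication". Section 6.2.2 gives the reason: "These restrictions result from potential confounding of efficacy or from drug interaction".

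**Scoring rule.** Protocol 12.5.1 addresses "Patients who received other concomitant medication having an effect on malaria for reasons other than rescue therapy". It and SAP 2.7.2.1 say that such patients "will be considered in the analysis as if they had not taken the drug". The examples are treatment of *P. vivax* and certain antibiotics. The sentence before it covers rescue for *P. falciparum*: those patients ("except for the treatment of a new infection) will be considered treatment failures".

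**Analysis set.** Uncorrected ACPR at Days 8, 15, 29 and 43 uses the FAS. Under SAP 2.2 the FAS needs any study drug and *P. falciparum* at screening. SAP 5.8 lists no FAS exclusion for a stopped course or a prohibited drug.

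**Handling elsewhere.** In the PCR-corrected Kaplan-Meier analysis, also on the FAS, patients who took antimalarials for reinfection or another non-rescue reason "will be censored at the first time of such antimalarial medications" (SAP 2.7.2.1.1). The PPS, used for by-visit PCR-corrected ACPR, excludes for PROH02, for PROH01A and for taking less than 80% of planned medication (SAP 5.8).

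**The concern.** The protocol restricts these drugs partly because they confound efficacy, and it stops the study course when they are used. The main scoring rule for uncorrected ACPR then sets that confounding aside. An infant who had part of the six-dose course and then another active drug, with negative films afterwards, is counted as cured by the study regimen.

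Uncorrected ACPR is the only by-visit cure rate on the full analysis set. Efficacy results also go to the DMC at interim assessment 1, before the decision on Cohort 2 (SAP 2.12). Compared with not crediting these infants, the rule can only leave the rate unchanged or raise it. The SAP has no analysis of this endpoint that would show by how much. Its one ACPR sensitivity analysis (2.7.2.1.2) removes early new infections from the PPS and does not bear on this.

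**Working it through.** **Step 1. One infant through each analysis.** Take an infant at dose level 2 who has 4 of 6 doses, is given a non-rescue antimalarial, is stopped under Table 6-2 and has negative films to Day 43. SAP 2.4.1 plans 12 tablets, so compliance is 8/12 = 66.7%.

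| Analysis | Set | Treatment of this infant |
|---|---|---|
| Uncorrected ACPR (SAP 2.7.2.1) | FAS | Drug ignored; success |
| PCR-corrected ACPR by visit (2.7.2.1) | PPS | Excluded: PROH02, and 66.7% is below 80% |
| PCR-corrected ACPR, Kaplan-Meier (2.7.2.1.1) | FAS | Censored at the drug |
| Recrudescence and new infection (2.7.2.2) | FAS, cleared by Day 7 | No censoring at the drug; counted as event-free follow-up |
| PCT and FCT (2.7.2.3) | FAS | Censored only at rescue; clearance after the drug counts |

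Two details. With 5 of 6 doses compliance is 10/12 = 83.3%, so only the PROH codes would remove the infant from the PPS. The Kaplan-Meier rule speaks of antimalarial medications and does not say whether an antibiotic with antimalarial activity is included.

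**Step 2. Can a failure definition catch the infant?** ETF, LCF and LPF (SAP 2.1.1.1) all require parasitaemia. With negative films none applies, and no rule makes a stopped course a failure.

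**Step 3. Denominator.** Protocol 12.8.2 and SAP 3.1.2 need 16 evaluable with 25% not evaluable: 16/(1 - 0.25) = 21.3, rounded up to 22. This reproduces the stated 22, used here as the approximate FAS size per cohort.

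**Step 4. Size.** One infant is 1/22 = 4.5 percentage points. Intervals are the plan's exact Clopper-Pearson 95% intervals; for 22/22 the lower limit is 0.025^(1/22) = 0.846. The number of affected infants, k, is an assumption, because the documents give no rate. Suppose all other infants are successes:

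| k | As written | If the k infants are scored as failures |
|---|---|---|
| 0 | 22/22 = 100% (84.6 to 100) | 22/22 = 100% (84.6 to 100) |
| 1 | 22/22 = 100% (84.6 to 100) | 21/22 = 95.5% (77.2 to 99.9) |
| 2 | 22/22 = 100% (84.6 to 100) | 20/22 = 90.9% (70.8 to 98.9) |

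**Step 5. Censoring against failure.** Take k = 2 with 18 successes among the other 20. As written: 20/22 = 90.9%. Scored as failures: 18/22 = 81.8% (59.7 to 94.8). If both are censored before the first failure and nobody else is censored, the Kaplan-Meier estimate is 18/20 = 90.0%. So failure scoring moves the rate by 9.1 points and censoring by 0.9. Step 4 is therefore the outer bound.

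**The case against.** **The trigger is narrow.** This stands. Doses fall at 0 to 60 hours, in hospital, with two staff observing each one, and antimalarial use in the previous 14 days is an exclusion. A course can be stopped only in that window. The scoring rule itself runs to Day 43, so it also covers a drug given after a complete course, but the part-treated case should be rare.

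**Some of these infants may be failures already.** This stands in part. An antimalarial given for the enrolled *P. falciparum* infection can be read as rescue, hence failure. The text does not settle it. Protocol 6.2.3 opens its list with "The following circumstances warrant discontinuation of study treatment" and names ETF, LCF and LPF. Sections 6.5.2 and 6.7.2 add a vomited repeat dose. None mentions treatment after a Table 6-2 stop. For *P. vivax*, later detection of another species is already a failure in uncorrected ACPR. A herbal product falls under the scoring rule only if it acts on malaria.

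**It is a pre-specified choice of estimand.** This stands against replacing the rule. Protocol and SAP agree, and failure scoring has its own bias: an infant clearing parasites who gets an incidental antibiotic would become a malaria failure. It does not stand against a sensitivity analysis. The existing FAS estimate with censoring is PCR-corrected and given for Days 29 and 43 only.

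**Stronger readings.** A reader might infer that uncorrected ACPR alone gives this credit. It does not: the incidence and clearance-time analyses do not censor at the drug either. A reader might also infer that 6.2.3 contradicts Table 6-2; on treatment after a stop it is silent, which is a gap.

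**Conclusion.** The point holds as a gap in the analysis plan. For uncorrected ACPR the main rule credits the study regimen with an outcome that another drug may have produced. The SAP handles the same infant differently in two other analyses and offers nothing to show the effect here.

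Each such infant is worth at most 4.5 points in a cohort of 22, and considerably less if the comparison is censoring. This rests on four conditions: a denominator near 22, an assumed 0 to 2 infants, negative later films, and the drug not being classed as rescue.

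A reader might infer that the trial's conclusion is at risk. The documents do not support that: the stated success criterion concerns artemether Cmax (SAP 2.5.2), and the secondary endpoints carry no pre-specified hypothesis (SAP 2.7.2).

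One wording mismatch stands apart from the scoring. The herbal row of Table 6-2 exempts rescue use, while 6.2.3 describes rescue as therapy with an effective antimalarial. These passages must be reconciled; no view is taken on the clinical rule.

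**What to change.** 1. Keep the rule in SAP 2.7.2.1 and protocol 12.5.1 as the main analysis.
2. Add a Kaplan-Meier estimate of uncorrected ACPR on the FAS at Days 8, 15, 29 and 43, censored at the first non-study antimalarial or antimicrobial with antimalarial activity given for a non-rescue reason. Take over only the drug-censoring rule of SAP 2.7.2.1.1; a new infection remains a failure here. State that antimicrobials are included.
3. Add a sensitivity table scoring these infants as failures from the first such dose, and report how many there are.
4. Apply the same censoring as a sensitivity analysis to recrudescence and new-infection incidence and to PCT and FCT.
5. State whether an antimalarial given for the enrolled *P. falciparum* infection after a Table 6-2 stop counts as rescue, and so as failure, in the analysis.
6. Reconcile the herbal row of Table 6-2 with the description of rescue in protocol 6.2.3.

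The cost is a few SAP sentences, some extra tables and a protocol wording change. The added estimates may be slightly lower than the main rate. No data collection is added: concomitant drugs and films are already recorded to Day 43.
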